Study Protocol

Official Title: Assessment of Periodic Screening of Women With Denser Breast Using WBUS and DBT (Also Known as "DBTUST-Dense Breast Tomosynthesis / Ultrasound Screening Trial")

ClinicalTrials.gov ID (NCT number): NCT02643966

Protocol Date: 5/11/2022

Scientific Background

Despite significant advancements in detection, diagnosis, and treatment, breast cancer remains one of the leading causes of death in women over the age of 40 [1, 2]. Across multiple randomized controlled trials (RCTs), mammography has been shown to reduce deaths due to breast cancer in women aged 40 to 74 [3]. There are subsets of women, however, where mammography is less effective. Invasive breast cancers are recognizable primarily as masses, areas of architectural distortion, and/or calcifications. Because masses are often similar in density to the breast parenchyma itself, dense breast tissue can mask cancer detection, with mammographic sensitivity of only approximately 50% in dense breasts [4-6]. Periodic mammography screening results in earlier detection of breast cancers and in the last two decades both mortality and, for many reasons including but not limited to earlier detection, morbidity of breast cancer has been steadily declining [7 -10]. However, there remains a serious and credible controversy as to the attributable benefit from mammography screening to this overall decline [11, 12]. Visually searching for and detecting breast abnormalities on any modality, but in mammography in particular, is difficult and time-consuming for radiologists due to the large volume of examinations and the low yield of detected cancers in the screening environment, in particular as related to mammograms of younger women with dense breasts. Therefore, a substantial fraction (>30%) of “detectable” breast abnormalities, including cancers that are retrospectively judged to be “visible” on mammograms, are initially completely missed (omission) or actually detected but unreported (commission) by radiologists [13-15]. The specificity of mammography is also relatively low for screening in that approximately 10% of women are recalled for additional imaging procedures and only a small fraction (15%-30%) of biopsies proves to be positive [16; 17]. Recall rates are even higher among younger women with dense breast tissue and for those women receiving their initial screening examination before a comparison to prior findings can be made [4; 5; 18-22]. To address reduced mammographic sensitivity in dense breasts, several imaging tests have been proposed as a replacement and/or for supplemental screening. Magnetic resonance imaging (MRI) has been recommended for supplemental screening in women at high risk because of genetic or familial history or prior radiation therapy to the chest before age 30 [23]. While MRI detects more cancers than even the combination of mammography plus ultrasound [6; 24-26], MRI is not well tolerated [27] or cost effective in broader populations [28], and there is currently “insufficient evidence” for or against its use in women at intermediate risk for reasons including breast density [23].

Large area size full-field digital detectors with high-resolution and wide latitude [29] enabled the development of advanced digital imaging techniques, such as digital breast tomosynthesis (DBT) [30] and breast computed tomography (CT) [31], that improve conspicuity of breast lesions by enabling the enhancement of lesion contrast and/or the provision of 3D non-overlapped tissue information at comparable radiation dose levels. Currently, several leading manufacturers are marketing and/or testing DBT systems. The DBT systems available to us are manufactured by Hologic Inc (Bedford, MA). The system acquires initially 15 low dose projection images (frames) and generates mathematically / reconstructs between 50 and 120 tomographic type slices with a non-isotropic voxel size of $125\mu\text{m} \times 125\mu\text{m} \times 1\text{mm}$ depending on the breast thickness during compression. DBT has been shown to improve performance substantially over FFDM in all breast densities, but, in particular, in women with density BIRADS 2 and 3 [32]. Interestingly, the vast majority of these improvements are in reducing recall rates while increasing the detection of invasive cancers [33-37]. With recent investigations on and approval of synthesized 2D reconstruction (C-View), the issue of added radiation dose when implementing a FFDM+DBT

screening practice is largely eliminated as the resulting procedure uses radiation exposure that is like that used in conventional FFDM. Hence, DBT is clearly a candidate for both baseline screening procedures, as well as for supplementary imaging, in particular as operationally the procedure is virtually identical to FFDM from a technologist's and a woman's perspective. The only meaningful operational difference is the increased time to interpretation (as compared with conventional FFDM based practice), which can be expected because of the large number of additional images generated by the procedure [38; 39]; however, it decreases substantially with experience [40]. Recent data on the performance of C-View alone has been published demonstrating comparable diagnostic performance to FFDM alone, as well as in conjunction with DBT [135, 136]. This comparable performance results in reducing radiation exposure to the screening population by approximately 45%, and allows for a DBT practice to be performed at comparable radiation dose to a conventional FFDM based practice.

Ultrasound is another test which has been considered for supplemental screening to FFDM of women with dense breasts [41]. Across eight single-center studies [5; 42-48] and three prospective multicenter trials [6; 49; 50], encompassing over 64,000 examinations, the supplemental cancer detection rate of ultrasound has consistently been approximately 2 to 4 per 1000. Across those series, over 90% of cancers seen only on ultrasound were invasive, with median size of ~10 mm. Among invasive cancers, where detailed [5; 6; 42; 43; 46; 49; 50], over 85% of invasive cancers seen only on ultrasound were node negative. While MRI will detect more cancers than ultrasound, the interval cancer rate with mammography plus ultrasound was only 8% after three years of screening mammography and ultrasound in the ACRIN 6666 study [6]; this rate compares favorably to those observed with mammography alone in fatty breasts [4; 51], where mammographic performance is close to being optimal. This suggests that, while additional cancers could be detected using MRI, the combination of ultrasound and mammography is sufficient. Importantly, 94% of cancers detected only with ultrasound were invasive, (96% of those were node negative, with a median size of ~10 mm [6]). The primary issues related to WBUS in large volumes are the needed professional resources (i.e., ,training, cost and practice complexity) and increasing recall rates [6; 22; 52]. In support of the aims of this proposal, at the recent Radiological Society of North America (RSNA) meeting a very preliminary report on the analysis of DBT supplemented by WBUS in the first cycle of WBUS was presented [139] and the results from 1039 examinations in a non-controlled environment confirmed that, as expected, WBUS detected approximately two additional cancers per 1000 examinations during this first WBUS cycle. There are no data available on repeat screening of this type of practice. Although there are little data on the performance of using WBUS alone for primary screening, this approach is being explored (primarily abroad) and is being assessed very preliminarily in this country as well [140]. Other recent published reports focus on comparing classification performance of DBT versus US of known abnormalities and/or include a very small number of cases [141-143]. Additional important supporting data are provided in the Preliminary Studies section later in the proposal.

There is currently a great interest in exploring practices that would increase screening efficacy in women with denser breasts who constitute a very large fraction of the screening population. WBUS and DBT are likely the most feasible approaches to replace and/or supplement screening in a large volume of women with denser breasts, because these approaches do not require injection of contrast and/or radioactive material. The objective is to demonstrate that using these technologies will increase screening efficacy in these women either by reducing recall rates or by improving cancer detection rates. Most important for future screening practices which are criticized for over-diagnosis is to increase the detection of those cancers who left alone would impact life expectancy

of the woman (as well as lifetime management cost). In this regard ultrasound seems to be doing significantly better than DBT, therefore, despite its higher recall rate, it may eventually prove to be either, as if not more efficacious than DBT as the primary screening modality in these women constituting approximately 45-50 percent of all screened women. Hence, assessing clinical utility of WBUS as either a supplementary modality or a primary screening modality is of utmost importance.

Study Objectives

The overriding objective is to perform a clinical study that would allow for assessing the performance of DBT alone versus DBT plus WBUS, and potentially WBUS serving as a primary screening modality.

Study Design & Methods

- 1) We will recruit sequentially approximately 6,200 women with known heterogeneously dense and/or primarily dense breast tissue (from a prior mammogram) who are scheduled to undergo routine mammography screening that includes a DBT examination.
- 2) Consenting women will undergo a DBT examination as part of their clinical exam and a WBUS examination.
- 3) DBT, WBUS, and a combination of both, will be independently reviewed and interpreted (Breast Imaging, Reporting and Data System rated) by experienced and specifically trained radiologists in a cross balanced (cases by mode and by reader) study design.
- 4) Using the results of the interpretations in a slightly modified “LOGICAL OR” mode, namely, the highest rating determines the recommendation/need for follow up, we will perform diagnostic work ups as needed (i.e., resulting from the “arbitration step”).
- 5) We will compare cancers and other benign abnormalities detected with DBT only to those detected with WBUS. We will compare rates of false positives as a result of interpreting DBT vs. WBUS vs. a combination of both, including recall for additional testing, short-interval follow-up rates and biopsy rates. We will assess positive predictive values (PPVs) and negative predictive values (NPVs). For marginal value assessment when utilizing both modalities, we will also assess the type of abnormalities detected by each modality, assuming that a larger study will be required to assess cancer detection rates by specific types.
- 6) We will analyze the impact of double reading DBT on cancer detection and false positive rates. We expect to show that double reading DBT+synthetic 2D will significantly improve cancer detection compared to single reading. We hope to show that this can be achieved with minimal increase in false positives.

Eligibility Criteria

Women aged 40 to 75 years of age with heterogeneously dense or extremely dense parenchyma by prior digital mammography report (i.e., “dense breasts”), presenting for routine annual mammography with digital breast tomosynthesis. For women who have not had any prior mammography (i.e. this is their first, baseline, mammogram), the breast tissue must be dense (heterogeneously dense or extremely dense) on the current mammogram.

Statistical Considerations

We will primarily compare rates of true positive and false positives findings induced by DBT vs. ABUS, including recall for additional testing, short-interval follow-up rates, biopsy rates. For marginal value assessment when utilizing both modalities, we will also assess the type of abnormalities detected by each modality, assuming that a larger study will be required to assess cancer detection rates by specific types.

Our secondary analysis will compare cancer detection and recall rates from single reading DBT vs. optimal double reading DBT (best pairs). We will compare the added cancer detection from double reading to that achieved with addition of screening ultrasound.

With over 12,000 examinations that had been double read and an expected yield of approximately 80 cancers, the limiting factor will be the assessment of cancer detection as a result of the double reading with arbitration. With an expected agreement rate of 50% we estimate that we will have a power of 78% to detect an increase of 15% or more in cancer detection rate in the experimental (double reading set) as compared with single readings. The analysis for changes in recall rates will have higher power because of the substantially larger number of cases being recalled (~1200).

References:

1. Mettlin C. Global breast cancer mortality statistics. *CA Cancer J Clin* , 1999; 49: pp. 135-137.
2. Smith R. Breast cancer screening among women younger than age 50: a current assessment of the issues. *CA Cancer J Clin*, 2000; 50: pp. 312-336.
5. Kolb T, Lichy J & Newhouse J. Comparison of the performance of screening mammography, physical examination, and breast US and evaluation of factors that influence them: an analysis of 27,825 patient evaluations. *Radiology*, 2002; 225(1): pp. 165-175.
9. Feig S. Increased benefit from shorter screening mammography intervals for women ages 40-49 years. *Cancer*, 1997; 80: pp. 2035-2039.

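### Does the plan need a follow-up rule for cancers found after a negative reading before it can report NPVs?

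*Combined protocol and SAP*

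**What the plan says.** Study Design & Methods, item 5, lists the comparisons of detected cancers and false positives and then adds "We will assess positive predictive values (PPVs) and negative predictive values (NPVs". This is the only mention of NPV as an output. Item 4 settles who goes to work-up: "the highest rating determines the recommendation/need for follow up, we will perform diagnostic work ups as needed". There, and in the short-interval follow-up rates of item 5 and Statistical Considerations, follow-up means management of a reading. It does not mean a search for cancers after a negative one.

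The size of the study comes from two places. Item 1 says "We will recruit sequentially approximately 6,200 women". The double-reading paragraph of Statistical Considerations begins "With over 12,000 examinations that had been double read and an expected yield of approximately 80 cancers" and refers to a "substantially larger number of cases being recalled (~1200". Eligibility Criteria describes women "presenting for routine annual mammography with digital breast tomosynthesis". The number of study rounds is not stated, and item 2 describes one DBT and one WBUS examination.

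Missed cancers appear only as background from another study: "the interval cancer rate with mammography plus ultrasound was only 8% after three years of screening mammography and ultrasound". The Scientific Background also says of ultrasound added to mammography that "the supplemental cancer detection rate of ultrasound has consistently been approximately 2 to 4 per 1000".

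Statistical Considerations makes the true-positive and false-positive comparison primary, and single against double reading of DBT secondary.

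**The concern.** An NPV needs to know whether examinations read as negative were truly free of cancer. Under item 4, a woman negative on every reading gets no work-up, so no cancer can be found in her at that screen. If only work-up cancers count, the NPV of the combined reading is 100% by construction.

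The number of screens appears to make this worse. With about two annual screens per woman, a cancer found at the second could be counted as a true positive of that screen only, or also as a false negative of the first. Under the second rule each woman's last examination has no later study screen, so a pooled NPV would mix two lengths of follow-up.

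NPV is what a woman with a negative result would be told, and the study objective includes WBUS as a possible primary screening test. A rule chosen after the data are seen could seem to let the analysts make the benefit of adding WBUS look large or small.

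**Working it through.** The plan states no NPV, false-negative rate or follow-up figure, so there is nothing of its own to reproduce. The check asks how far the choice of rule moves NPV, and whether it moves the comparison between modes.

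**Inputs**
- 6,200 women (item 1); 12,000 examinations, 80 cancers and 1,200 recalls (double-reading paragraph).
- Recall 1,200/12,000 = 10%.
- Examinations per woman 12,000/6,200 = 1.94, read as two screens (inference). Second-screen examinations 12,000 − 6,200 = 5,800.
- Assumed: 8% of cancers missed by all readings, borrowed from the background study, with 5 to 15% as the range.
- Assumed: first-screen yield per examination 1 to 2 times the second-screen yield.
- Assumed: second-screen cancers are no commoner in women recalled at the first screen, and the combination misses only what every reading missed.
- WBUS-only cancers 2 to 4 per 1000 (Scientific Background).

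**First-screen negatives:** 6,200 × 0.9 = 5,580, used for every mode as a simplification.

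**Narrow rule (only cancers before the next screen)**
- Missed by all: 80/0.92 − 80 = 6.96.
- First-screen share: 6.96 × 6,200/12,000 = 3.6.
- Rate: 3.6/5,580 = 0.64 per 1000.

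**Broad rule (second-screen cancers also count)**
- Second-screen cancers at equal yield: 80 × 5,800/12,000 = 38.7.
- With first-screen yield doubled: 80 × 5,800/(2 × 6,200 + 5,800) = 25.5.
- In first-screen negatives: × 0.9 = 34.8 and 22.9.
- Rates: (3.6 + 22.9)/5,580 = 4.8 and (3.6 + 34.8)/5,580 = 6.9 per 1000.
- Ratio to the narrow rule: 4.76/0.64 = 7.4 and 6.88/0.64 = 10.7.

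**Sensitivity to the missed share**
- At 5%, first-screen misses are 2.18: (2.18 + 22.9)/2.18 = 11.5 and (2.18 + 34.8)/2.18 = 17.0.
- At 15%, they are 7.29: (7.29 + 22.9)/7.29 = 4.1 and (7.29 + 34.8)/7.29 = 5.8.

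The fold change therefore runs from about 4 to 17, and 7 to 11 is its value at 8% only.

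**The same results as NPV**

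WBUS-only cancers at the first screen number 6,200 × 0.002 = 12.4 to 6,200 × 0.004 = 24.8, or 2.2 to 4.4 per 1000 DBT negatives.

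| Rule | DBT plus WBUS | DBT alone | Difference per 1000 | NPV ratio |
|---|---|---|---|---|
| Narrow | 99.94% | 99.49 to 99.71% | 2.2 to 4.4 | 1.002 to 1.004 |
| Broad | 99.31 to 99.52% | 98.87 to 99.30% | 2.2 to 4.4 | 1.002 to 1.004 |

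The broad rule adds the same term to both modes (22.9/5,580 = 0.41 to 34.8/5,580 = 0.62 percentage points), so it cancels from the difference. At 4.4 per 1000 the ratio is 99.936/99.491 = 1.0045 under the narrow rule and 99.312/98.868 = 1.0045 under the broad one.

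**What does move:** the ratio of missed cancers, that is of 1 − NPV, for DBT alone against the combination.
- Narrow: (12.4 + 3.6)/3.6 = 4.4 to (24.8 + 3.6)/3.6 = 7.9.
- Broad: (12.4 + 38.4)/38.4 = 1.3 to (24.8 + 26.5)/26.5 = 1.9.

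The plan does not propose to report that ratio.

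**The case for a change.** The best case for a change is that the plan promises a quantity it cannot compute from what it describes, and that one added sentence would settle it. The inference of two screens is also reasonable: the title speaks of periodic screening, the double-reading analysis concerns DBT, and 10% recall agrees with the rate given in the Scientific Background. Even with one round, the follow-up period would still be undefined. The missed-cancer ratio also separates the two rules clearly: over a 5 to 15% missed share it is 2.7 to 12.4 under the narrow rule and 1.3 to 2.0 under the broad one.

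The gap itself stands. The consequence is weaker than it looks. The large fold change rests on a missed share from a study of mammography plus ultrasound, on an assumed split of cancers between rounds, and on cancer and recall totals taken from a paragraph about double reading. The 2 to 4 per 1000 is ultrasound added to mammography; for ultrasound added to DBT the same section reports about two, which makes the missed-cancer ratio 4.4 against 1.3 to 1.5. If the 12,000 instead counted one DBT and one WBUS per woman (6,200 × 2 = 12,400), the next-screen rule would not arise within the study.

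The plan also states no wrong rule. Its only measure of missed cancers is an interval cancer rate, and nothing in it suggests charging next-screen cancers to the earlier reading.

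**Conclusion.** No change to the plan follows. This is an omitted reporting definition of a kind that analysts ordinarily supply: a stated follow-up period, with NPV computed on the examinations that have it. A reader of the results needs that definition to interpret the NPV level, but the conclusions the trial is built to reach do not depend on it.

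On the assumptions above, the choice of rule moves the NPV by 0.4 to 0.6 percentage points. The absolute difference and the ratio of NPVs between DBT alone and DBT plus WBUS stay essentially the same. The several-fold change appears only in missed cancers per 1000 negatives and in the ratio of 1 − NPV. It depends on an inferred second screen and a borrowed missed share (about 4- to 17-fold over 5 to 15%). The primary true-positive and false-positive comparison and the secondary double-reading comparison are not affected.

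### The secondary analysis is planned on the best reader pairs, while the aim and the stated 78% power concern double reading in general; make the all-pairs comparison the secondary analysis

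*Combined protocol and SAP*

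**What the plan says.** Three places in the combined protocol and SAP describe the double-reading question.

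- **Aim** (Study Design & Methods, item 6): "We expect to show that double reading DBT+synthetic 2D will significantly improve cancer detection compared to single reading". Reader pairs are not mentioned.
- **Planned analysis** (Statistical Considerations, secondary analysis): "Our secondary analysis will compare cancer detection and recall rates from single reading DBT vs. optimal double reading DBT (best pairs"). This is the only mention of best pairs. The same paragraph adds: "We will compare the added cancer detection from double reading to that achieved with addition of screening ultrasound". It does not say which double-reading gain is meant.
- **Power** (Statistical Considerations, last paragraph): the base is given as "With over 12,000 examinations that had been double read", with about 80 cancers expected, and "the limiting factor will be the assessment of cancer detection as a result of the double reading with arbitration". Then: "With an expected agreement rate of 50% we estimate that we will have a power of 78% to detect an increase of 15" percent or more, "in the experimental (double reading set) as compared with single readings".

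The documents do not give the measure by which a pair is best, the number of readers or pairs, when the choice is made, which examinations the chosen pairs cover, or whether the same reads serve for both choosing and testing.

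**The concern.** The aim and the power describe one comparison (arbitrated double reading against single reading), and the planned analysis names a narrower one (best pairs against single reading). No sentence connects them. Two consequences follow.

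First, the quantity estimated changes. A clinic that adopts double reading gets the pairs it has, so a result confined to the best pairs does not answer the question in item 6, however the pairs were chosen.

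Second, a label such as optimal or best invites a choice based on performance. If performance is judged on the reads that are then tested, chance differences between pairs are counted as benefit. That could carry into the comparison with ultrasound: if the best-pairs gain is the one used there, the comparison tilts toward double reading. A reader could also attach the 78% to an analysis for which it was not stated.

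**Working it through.** **1. The plan's own power figure.** From the documents: about 80 cancers, 50% agreement, an increase of 15%, power 78%. Assumed, because not stated: two-sided 5% test, and 15% meaning 15 percentage points. The usual paired (McNemar) formula with discordance ψ and net gain d is

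Power = Φ[(d√n − 1.96√ψ) / √(ψ − d²)].

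With n = 80, d = 0.15 and ψ = 0.25:

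- numerator: 0.15 × 8.944 − 1.96 × 0.5 = 1.342 − 0.980 = 0.362
- denominator: √(0.25 − 0.0225) = 0.477
- Φ(0.362 / 0.477) = Φ(0.758) = 0.776, or 78%.

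The same value comes from a one-sample test of 0.50 against 0.65 on 80 cancers, which is algebraically identical. The figure is therefore reached with all of the roughly 80 cancers, and no selection of pairs enters it. The value ψ = 0.25 is used below only because it matches the plan's figure.

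**2. What choosing pairs on the tested reads could do.** The documents give no reader numbers, so this is hypothetical. Assume no true gain, 80 cancers split evenly over k pairs, and the pairs with the largest observed net gain kept and pooled.

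Hand check for k = 6, keeping 3, ψ = 0.25:

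- cancers per pair: 80 / 6 = 13.3
- standard error of one pair's net gain: √(0.25 / 13.3) = 0.137
- expected values of the three largest of six standard normal draws: 1.267, 0.642, 0.202; mean 0.704
- apparent gain: 0.704 × 0.137 = 0.096, about 10 points.

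Simulation (40,000 runs per setting) gives 9.5 points for this case. Apparent gain in percentage points when the true gain is zero:

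| Discordance | 2 of 3 pairs kept | 3 of 6 | 5 of 10 | 8 of 15 |
|---|---|---|---|---|
| 5% | 1.7 | 3.7 | 4.2 | 4.2 |
| 10% | 2.5 | 5.8 | 7.3 | 7.7 |
| 25% | 4.1 | 9.5 | 12.7 | 14.6 |

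With all 80 cancers and no selection, the apparent gain is 0.0 at each discordance.

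**3. What removes the bias.** When pairs are chosen in one half of the reads and tested in the other (ψ = 0.25, no true gain), the apparent gain is within 0.1 point of zero. The price is precision. Half the reads and half the pairs leave 80 × ½ × ½ = 20 cancers, with a standard error of √(0.25 / 20) = 0.112 (about ±22 points at 95%). All 80 cancers give √(0.25 / 80) = 0.056 (about ±11 points).

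**The case against.** The strongest reply is that nothing here is contradictory. A general aim, a more specific operational phrase and a power paragraph can coexist, and the power paragraph does not say that best pairs are excluded from its double-reading set. Best pairs might be fixed in advance, or be an openly labelled best case. This stands in part: the text shows an undefined comparison that is not tied to the aim or the power, not two statements that cannot both be true. It does not remove the point, because a best-pairs gain differs from the general gain even when the pairs are chosen properly.

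Three stronger readings are tempting, and the documents do not support them.

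- *The pairs will be picked on the same reads.* The past tense about examinations already double read suggests that reads may exist, but the same paragraph speaks of an expected yield and of power still to come. The selection method is simply not given.
- *The analysis is underpowered.* That would need best pairs to cover fewer than about 80 cancers, which no sentence says. A larger true gain in good pairs could also offset a smaller number.
- *Double reading can only add cancers, because* "the highest rating determines the recommendation/need for follow up". In item 4 of Study Design & Methods that rule concerns DBT, WBUS and their combination. It is not stated as the rule for double reading of DBT, so no figure here relies on it.

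The size of the bias also rests entirely on assumed reader numbers and discordance, and in the mildest settings it is about 2 points. How the 50% agreement should be read is a separate question and adds no weight here.

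**Conclusion.** The point holds as a cheap improvement to the secondary analysis. The textual part needs no assumption: the aim and the only stated power concern arbitrated double reading, the planned comparison is best pairs, and no selection rule or link is given. The upward bias is conditional on pairs being chosen by their results on the tested reads. Under that condition, and with no true gain, it is about 10 points in the six-pair example against a target effect of 15. Across the settings tried it runs from about 2 to about 15 points, growing with the number of pairs and with discordance. A contradiction, a loss of power and an actual data-driven choice are not established. The primary comparison of DBT with ABUS is not touched.

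**What to change.** In Statistical Considerations, define the secondary analysis as cancer detection and recall with a single DBT reading versus double reading with arbitration, over all reader pairs and all double-read examinations (about 80 cancers). State that the 78% refers to this comparison, and that this all-pairs gain is the one set against the gain from adding ultrasound.

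Keep best pairs as an exploratory analysis under a written rule. Either name the pairs in advance, or choose them by cross-validation so that no read is used both to select and to test. If the sponsor prefers to keep best pairs as the secondary analysis, the plan should define them and restate the power for that comparison.

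Cost: wording and at most one reanalysis of the double reads, with no extra patients or readings. The reported double-reading gain may look smaller, and a cross-validated best-pairs estimate will be imprecise, which is why it belongs among the exploratory results. Pairs fixed in advance avoid the split.
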